5.2 Secondary Outcomes

- Evaluation of the inter-reader reproducibility in healthy subjects with High-Res-OCT
- Evaluation whether pathological changes seen in SD-OCT or color fundus photography correlate with changes seen in High-Res-OCT. Here, a binary readout, i.e pathology present (yes/no) will be used.
- Subgroup analysis will be performed with patients suffering from diabetic retinopathy, artery and vein occlusion, retinal detachment, glaucoma, optic nerve neuropathy, hereditary retinal diseases, age related macular degeneration, retinal changes from arterial hypertension and uveitis
- Evaluation of the intra-and inter-reader reproducibility in the diagnosis (binary) using High-Res-OCT
- Evaluation of the segmentation quality of the retinal layers using High-Res-OCT. For this purpose the discrimination capacity between the different retinal layers will be assessed, especially in the healthy group. For this purpose, a binary outcome will also result.

5.3 Other Outcomes of Interest

Exploratory outcome include:

- Usefulness of colored infrared images using the Mutlicolorimaging software compared to color fundus photography

5.4 Safety Outcomes

As this is a CE certified device with minimal safety concerns we do not plan to study safety outcomes with this device.

6. CLINICAL INVESTIGATION DESIGN

6.1 General clinical investigation design and justification of design

This trial is a prospective clinical study. Patients, who fulfilled the inclusion criteria will be recruited at the Inselspital Bern. Study data will be collected in REDCap®, a secure, and validated web application for building and managing online surveys and databases. Study participants will undergo imaging of one or both eyes in accordance with the clinical indication, which will last approximately 30-60 seconds per eye. The imaging process is without any contact and pharmacologic dilatation of the pupils will not be used for the purposes of this study.

We plan to include approximately 550 participants in the study, including 100 healthy participants and 450 patients with diagnosed ocular disorders, including diabetic retinopathy (50 patients), artery and vein occlusion (50 patients), glaucoma (50 patients), optic nerve neuropathy (50 patients), hereditary retinal diseases/dystrophies (50 patients), retinal detachment (50 patients), age related macular degeneration (50 patients), retinal changes from arterial hypertension (50 patients), uveitis (50 patients).

Study participants will undergo imaging with High-Resolution OCT only within a single imaging session on a single day. Additionally, study participants will be asked to consent to prospective collection of clinical and demographic data, to correlate findings of High-Resolution OCT imaging to subsequent clinical course. Data from the clinical records are to be used for the study up to the time of the visit.

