5. CLINICAL INVESTIGATION OUTCOMES

5.1 Primary Outcome

The primary outcome as measured on the individual patient-level is whether High-Resolution OCT has a similar or higher specificity and sensitivity to detect pathological changes in the retina/optic nerve as conventional imaging methods, such as SD-OCT, color fundus photography and fluorescein angiography. This will result in a binary outcome. Pathological morphological changes includes but are not limited to, intraretinal or subretinal fluid, epiretinal membrane, substance defect, drusen, hyperreflective foci, atrophy, neovascularization, optic nerve swelling, choroid abnormalities, scars, ischemia. Additionally, study participants will be asked to consent to prospective collection of clinical and demographic data, to correlate findings of High-Resolution OCT imaging to subsequent clinical course.

Ophthalmic diseases include, but are not limited to:

- Retinal vascular diseases
- Retinal detachment
- Hereditary retinal diseases/dystrophies
- Glaucoma
- Optic nerve neuropathy
- Inflammatory/infectious retinal diseases

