9.2.1 Assessment of primary outcome

The sensitivity and specificity of the High-Resolution OCT to diagnose the presence/absence of pathological changes in the retina/optic nerve in comparison to conventional imaging modalities will be assessed as a primary outcome. The following pathological changes will be assessed: intraretinal or subretinal fluid, pigment epithelial detachment, epiretinal membrane, substance defect, drusen, hyperreflective foci, atrophy, neovascularization, choroid abnormalities, scars, optic nerve swelling and ischemia. For each of these pathological changes a binary outcome will result. Additionally, study participants will be asked to consent to prospective collection of clinical and demographic data, to correlate findings of High-Res-OCT imaging to subsequent clinical course.

There is no need to be in a particular posture before the examination in order to obtain high quality images. The participants will be in a sitting position during the examination during approximately 30-60 seconds per eye. In case the measurement needs to be repeated, no waiting period will be necessary. A repeated measurement needs to be recorded in the CRF.

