11.5 Handling of missing data and drop-outs

All data from all participants included in the study will be analyzed.

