12.1.2 Specification of source data and source documents

Source data will be available at the site to document the existence of the investigation subjects. Source data will include the original documents relating to the investigation, as well as the medical treatment and medical history of the subject.

The source documents include:

- Demographic form: Study ID, study eye, personal information (year of birth, age, sex), eye anamnesis (diagnosis, date of diagnosis, recurrences). Data will be entered electronically in REDcap.
- Examination form (data from both eyes): visit date and if applicable, visual acuity, SD-OCT; FA, ICG, FAF plus additional information if required (correction). Data will be entered electronically in REDcap.
- Informed consent form; stored in a locked cupboard.

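### The number of eyes imaged varies by indication, but the analysis plan has no study-eye rule, same-eye pairing or allowance for correlation within a patient

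*Combined protocol and SAP*

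**What the plan says.** On imaging, section 6.1 states: "Study participants will undergo imaging of one or both eyes in accordance with the clinical indication". The number of eyes per participant is therefore one or two and follows clinical status.

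On the outcome, section 5.1 states: "The primary outcome as measured on the individual patient-level is whether High-Resolution OCT has a similar or higher specificity and sensitivity" to conventional imaging. Section 9.2.1 lists the pathological changes and adds: "For each of these pathological changes a binary outcome will result".

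On data capture, section 12.1.2 lists two forms. One is "Examination form (data from both eyes): visit date and if applicable, visual acuity" and further imaging. The other is "Demographic form: Study ID, study eye, personal information (year of birth, age, sex" and so on. A study eye is thus recorded, but no section says how it is chosen.

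On the data used, section 11.5 states: "All data from all participants included in the study will be analyzed".

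Sections 11.1 to 11.5 say nothing about eyes. Section 11.4 calls for a one-sided 95% confidence interval without naming a method. Section 11.4.1, on datasets and analysis populations, defines no unit of analysis. Section 11.4.2 names ROC and precision-recall curves computed in Scikit-learn. Section 11.2 counts the 550 in patients.

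**The concern.** A patient-level outcome from a study that may image two eyes needs one of two things: a rule that picks one eye, or a rule that turns two eyes into one result. An eye-level analysis needs a method that recognises that two eyes of one person are not independent. The plan gives none of these, and 11.4.5 allows the analysis to be adapted while it is under way, so the unit could be settled after the data have been seen.

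Two things are at stake. If both eyes are combined into one patient result, one-eye and two-eye patients have different chances of a positive call, and the pooled sensitivity and specificity mix the two. Because the number of eyes follows indication, it probably differs between the nine disease groups and the healthy group, which clouds comparison across them. A combined result can also hide disagreement: a finding in the right eye on SD-OCT and in the left eye on High-Res-OCT would count as agreement. If eyes are instead pooled as if independent, the point estimate may be sound but its interval is too narrow, and the one-sided 5% error on which the comparison rests is exceeded.

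**Working it through.** **The plan's own figure.** The plan has no eye-level figure to reproduce. Its 550 equals the recruitment total, 100 + 9 × 50. The precision inputs in 11.4.2 give 1.96² × 0.9 × 0.1 / 0.03² / 0.9 ≈ 427 at 95% confidence, so they do not reproduce 550. That is a separate matter, and nothing below depends on it.

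**Inputs.** From the documents: one or two eyes per participant (6.1), 450 patients with disease (6.1), one-sided 5% error (11.2), and 90% accuracy of conventional imaging (11.2). Assumed, because the documents do not give them:
- sensitivity and specificity of 0.90 per eye, borrowed from the 90% accuracy;
- the correlation ρ between the two eyes of a patient;
- the share f of patients with both eyes imaged.

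**Route 1: a patient is positive if either eye is positive.** The plan does not state this rule. It is one natural way to use both eyes.

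Two-eye specificity = Sp² + ρ·Sp·(1 − Sp) = 0.81 + 0.09ρ

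- ρ = 0: 0.81
- ρ = 0.5: 0.855
- ρ = 1: 0.90

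Two-eye sensitivity, both eyes diseased = 1 − [(1 − Se)² + ρ·Se·(1 − Se)] = 0.99 − 0.09ρ, which is 0.99, 0.945 and 0.90 at the same three values.

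One-eye patients stay at 0.90. With half the patients imaged in both eyes, overall specificity is 0.5 × 0.90 + 0.5 × 0.81 = 0.855 at ρ = 0, and 0.5 × 0.90 + 0.5 × 0.855 ≈ 0.878 at ρ = 0.5.

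**Route 2: eyes pooled as independent.** N patients give N(1 + f) eyes. The true variance of the total exceeds the naive one by 2fNρ in units of the per-eye variance, so

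design effect D = 1 + 2fρ/(1 + f)

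True one-sided error = 1 − Φ(1.645/√D). True coverage of a nominal two-sided 95% interval = 2Φ(1.96/√D) − 1.

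| f | ρ | D | One-sided error | Coverage |
|---|---|---|---|---|
| 0.25 | 0.1 | 1.04 | 5.3% | 94.5% |
| 0.5 | 0.3 | 1.20 | 6.7% | 92.6% |
| 0.5 | 0.5 | 1.33 | 7.7% | 91.0% |
| 1 | 0.3 | 1.30 | 7.5% | 91.4% |
| 1 | 0.5 | 1.50 | 9.0% | 89.0% |

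For sensitivity in 450 diseased patients at ρ = 0.5, the naive 95% half-width is 0.0226 against a true 0.0261 when half have both eyes imaged, and 0.0196 against 0.0240 when all do.

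**Information is not lost.** With 450 patients, f = 0.5 and ρ = 0.5, the 675 eyes are worth 675/1.333 ≈ 506 independent eyes, which is still more than 450. The fault lies in the stated error, not in power.

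**The case against.** The strongest reply is that the plan already points to one eye per patient. The outcome is at patient level, the sample size is counted in patients, and a study eye is recorded. That analysis would remove both problems. It is a fair reading of 5.1 and 12.1.2, but section 11 never adopts it and no selection rule is given. The case report form is a separate appendix that is not among these documents, so whether it defines the study eye cannot be checked.

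Second, support for pooling eyes is thin. Section 11.5 falls under missing data and drop-outs and speaks of participants, not eyes. The examination form in 12.1.2 is a source document, not an analysis set. Pooling would also depart from 5.1. This stands, so Route 2 is conditional.

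Third, both modalities may shift together under an either-eye rule, leaving their difference less affected. This also stands in part. But the primary objective in 4.2 concerns sensitivity and specificity themselves. Section 9.1 leaves the comparator to clinical routine without requiring that both modalities cover the same eyes, so cancellation is not assured.

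Three stronger readings are tempting, and the documents do not support them:
- A reader might infer that every way of following the plan gives a wrong estimate or a wrong interval. The one-study-eye analysis does not.
- A reader might infer that an either-eye rule also breaks the 5% error. It does not: it yields one result per patient, patients are independent, and the patient-level difference keeps its nominal error. What changes is the quantity being estimated.
- A reader might quote an error of 10.4% as the size of the problem. That needs pooled eyes, two eyes in every patient, and a correlation of 0.7 taken from a single modality. Section 6.1 says the number of eyes varies, and for the paired comparison the correlation that matters is that of the within-eye differences, which may be smaller.

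**Conclusion.** The gap is real and should be closed before analysis. The plan collects a variable number of eyes, reports per patient, and does not say how one leads to the other. Under an either-eye rule, two-eye specificity is 0 to 9 percentage points below the one-eye value, and sensitivity with both eyes diseased is 0 to 9 points above it, with a smaller shift likely in the difference between modalities. If eyes are pooled as independent, the one-sided error is about 6.7-7.7% with half the patients imaged in both eyes and 7.5-9.0% with all, for correlations of 0.3 to 0.5. It is nearer 5% if few patients have two eyes imaged or if within-eye differences are weakly correlated. These sizes rest on assumed per-eye accuracy, correlation and share of two-eye patients. The direction of the pooling error holds for any positive correlation. The documents do not show that either route has been chosen, only that neither is excluded.

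**What to change.** In 5.1 and 11.4.2:
- Compare High-Res-OCT with the comparator in the same eye, using all eyes imaged with both modalities.
- Compute intervals clustered by patient, by GEE or a bootstrap that resamples patients.
- Amend the patient-level wording in 5.1 so that the outcome and the analysis use the same unit.
- Report a one-study-eye-per-patient analysis alongside, with the selection rule written down in advance.

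The last item is more than a formality. Clustering corrects the variance but not the weighting: an eye-level estimate counts two-eye patients twice, and the number of eyes follows indication. The one-eye analysis shows whether that extra weight changes the result.

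The cost is protocol wording and a few lines of code, since the examination form already provides for both eyes. Intervals will be slightly wider than under naive pooling, and eyes imaged with only one modality drop out of the paired comparison.

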4. CLINICAL INVESTIGATION OBJECTIVES

4.1 Overall Objective

The study aim is to investigate the diagnostic accuracy of the High-Resolution OCT in comparison with conventional imaging methods and whether High-Resolution OCT can reliably diagnose retinopathies thereby making more invasive investigations such as fluorescein angiography or conventional imaging methods futile. The main goal is to facilitate diagnosis of eye diseases for individual patients.

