7. CLINICAL INVESTIGATION POPULATION

7.1 Eligibility criteria

Subjects fulfilling all of the following inclusion criteria are eligible for the investigation:

- Informed Consent signed by the subject
 - Patients and healthy subjects from the Department of Ophthalmology, University Hospital Bern requiring conventional imaging for eye disease
 - Patients of 18 years or older

The presence of any one of the following exclusion criteria will lead to the exclusion of the subject

- Patients not willing or able to sign informed consent
- Patients younger than 18 years
- Contraindication and limitation of the MD as described in the instructions for use: Patients with epilepsy.
- Vulnerable subjects (except the objectives of the investigation concern vulnerable subjects specifically),
- Inability to follow the procedures of the investigation, e.g. due to language problems, psychological disorders, dementia, etc. of the subject
- Participation in another investigation with an investigational drug or another MD within the 30 days preceding and during the present investigation
- Enrolment of the PI, his/her family members, employees and other dependent persons

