7.2 Recruitment and screening

There will be a consecutive ongoing recruitment of patients and healthy subjects attending routine follow-ups through the involved investigators in daily clinical practice at Department of Ophthalmology, Inselspital, Bern. Recruitment will last from October 2021 to November 2023. Subjects will be given enough time (hours to days) to consider and to council with relatives and experts. No screening requirements is necessary (laboratory or other diagnostic tests). There will be no payment or compensation given to subjects.

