9. CLINICAL INVESTIGATION ASSESSMENTS

9.1 Clinical investigation flow chart(s) / table of clinical investigation procedures and assessments

There will be a consecutive ongoing recruitment of patients and healthy subjects attending routine follow-ups through the involved investigators in daily clinical practice at Department of Ophthalmology, Inselspital, Bern. Recruitment will last from October 2021 to November 2023. Patients, who fulfilled the indication of either SD-OCT or fluorescein angiography imaging for diagnosis of retinal/optic nerve disease will be included and additional imaging will be performed with the High-Res-OCT.

Subject	Initial imaging with High-Res-OCT
Healthy volunteers	X ₁
Patients with retinal/optic nerve disease	X ₁
X =mandatory imaging session. ¹ routine imaging with either SD-OCT, fundus photography or fluorescein angiography according to clinical routine	

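### Entry rules mix already diagnosed patients with patients imaged to reach a diagnosis, so the planned data do not support the diagnostic and replacement conclusion in section 4.1

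*Combined protocol and SAP*

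**What the plan says.** The protocol describes who enters in five places, and they do not match.

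- **6.1** plans "100 healthy participants and 450 patients with diagnosed ocular disorders", with 50 patients in each of nine named disease groups.
- **7.1** asks only that participants, patients and healthy alike, come from the department "requiring conventional imaging for eye disease". It neither requires nor excludes a prior diagnosis.
- **7.2** plans "consecutive ongoing recruitment of patients and healthy subjects attending routine follow-ups".
- **7.3** places each participant in one of the 6.1 disease categories or calls them healthy. It does not say when, or on what basis, the diagnosis was made.
- **9.1** repeats the follow-up setting and then adds: "Patients, who fulfilled the indication of either SD-OCT or fluorescein angiography imaging for diagnosis of retinal/optic nerve disease will be included". Its table lists healthy volunteers.

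The overall objective in 4.1 includes "whether High-Resolution OCT can reliably diagnose retinopathies thereby making more invasive investigations such as fluorescein angiography or conventional imaging methods futile". The primary outcome in 9.2.1 is narrower: presence or absence of each of a list of lesions, compared with conventional imaging.

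Under 12.1.2 the demographic form records "eye anamnesis (diagnosis, date of diagnosis, recurrences", and the examination form records the visit date. Sections 6.1 and 9.3 limit clinical records to those available up to the visit. Section 6.2 describes an open-label study and 6.2.2 plans no blinding.

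**The concern.** Section 4.1 concerns patients whose diagnosis is still open, because only for them could a new scan replace angiography in the work-up. Sections 6.1 and 7.2, read plainly, fill the study with people whose disease is already known and add a healthy group. Known disease is usually easier to recognise than disease under suspicion, and healthy eyes are easier to clear than eyes that prompted suspicion. Sensitivity and specificity from such a mix therefore tend to be too high for the diagnostic setting.

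Two investigators could also follow different sections and enrol different populations, and no planned analysis would show it. At stake is the headline conclusion: a good result in known cases could be reported as evidence that angiography or conventional imaging is no longer needed.

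**Working it through.** **1. The plan's own figure.** From 6.1: 9 × 50 = 450 patients; 450 + 100 healthy = 550. The recruitment total reproduces. The case share is 450/550 = 81.8%, fixed by quota. (Section 11.4.2 assumes a prevalence of 0.9. Neither that difference nor the derivation of 550 as a sample size matters for this point.)

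**2. Four kinds of participant against the entry texts.**

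- *Known disease, at follow-up.* Fits 6.1, 7.2 and 7.3, and 7.1 if imaging is needed. Fits the second part of 9.1 only if monitoring scans count as imaging for diagnosis.
- *Diagnosed for the first time at the visit.* Fits 7.1, 7.3 and 9.1. Fits 6.1 only if a same-day diagnosis counts, and 7.2 only if the patient was already attending follow-up.
- *Imaged for suspicion, then cleared or left unresolved.* Fits 7.1 and the second part of 9.1. Has no place in the nine groups of 6.1 and no category in 7.3, unless counted as healthy.
- *Healthy volunteer.* Fits 6.1 and the 9.1 table. Fits 7.1 only if conventional imaging for eye disease is needed.

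The third kind is needed to estimate specificity in the diagnostic setting, and the plan provides no slot for it.

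**3. What the pooled estimate measures.** Let S_E be sensitivity in established disease, S_N sensitivity in diseased patients with no diagnosis before the visit, and w the share of diseased participants who are established. Then

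pooled S = w·S_E + (1 − w)·S_N, so pooled S − S_N = w·(S_E − S_N).

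Under a literal reading of 6.1, w = 1. The data then contain nothing on S_N, and the whole gap S_E − S_N goes unseen. Under 9.1 read alone, w could be much lower. The documents give none of w, S_E or S_N. A positive gap is the usual expectation, but its size cannot be computed. The same reasoning applies to specificity in healthy eyes as against suspected but disease-free eyes.

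**4. Precision if results are split by prior diagnosis.** At the sensitivity of 90% used in 11.4.2, the 95% half-width is 1.96 × √(0.9 × 0.1/n):

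- n = 450: 2.8 points
- n = 100: 5.9 points
- n = 50: 8.3 points

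To reach the 0.03 margin of error in 11.4.2 within one stratum, n = 1.96² × 0.09/0.03² = 385 diseased patients (rounded up). The number of patients who will have no prior diagnosis is not stated, so 50 and 100 are illustrations.

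**The case against.** **Newly diagnosed patients can enter.** Section 7.1 does not demand a prior diagnosis and 7.3 does not date it. This stands. A reader might infer that the study cannot yield any diagnostic evidence, but the documents do not go that far. They show that the plan neither secures such patients nor separates them.

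**The primary outcome is lesion detection, not the disease label.** This also stands. A within-patient comparison of lesion detection is possible in known disease. It supports a statement about detecting changes in known disease, not one about replacing the diagnostic work-up.

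**A reader might infer that case selection favours conventional imaging.** Section 8.1.2 calls SD-OCT, colour fundus imaging and angiography the routine examinations for retinal pathology, so entry diagnoses may often rest on them. Suppose both methods truly detect 90%, every case entered on a positive conventional image, and that result persists. Conventional sensitivity becomes 100%. High-Res-OCT becomes P(both positive)/0.90: 0.80/0.90 = 88.9% if misses never coincide, 0.81/0.90 = 90% if they are independent, and 0.90/0.90 = 100% if they always coincide. The apparent deficit is 0 to 11 points. If half the cases were selected this way, with independent misses, it is 95% − 90% = 5 points. The documents do not support using these figures, for four reasons:

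- Entry under a disease label does not make conventional imaging positive for every listed lesion, so the 100% does not transfer to the lesion-level endpoint.
- The basis of the entry diagnoses is not stated. Section 2.2 calls the comparators standard for vascular disease, while the groups include glaucoma and optic nerve neuropathy.
- Persistence of findings is unsupported in follow-up patients.
- Unmasked readers could push the result towards High-Res-OCT.

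**No independent reference standard is named.** This is a separate and more basic gap. Changing the entry rule does not close it.

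**Conclusion.** The point holds as a limit on interpretation. The entry population is described inconsistently. Under the most direct reading of 6.1, all 450 patients (81.8% of participants) carry a diagnosis already and none of the ten categories (nine diseases plus healthy) holds suspected disease. Such data estimate lesion detection in known disease and healthy eyes. They do not support the reliable-diagnosis and replacement statement in 4.1, and will tend to flatter accuracy for patients still awaiting a diagnosis. That tendency rests on the usual expectation that established disease is easier to recognise. Its size is not recoverable from the documents.

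If entry diagnoses came from the comparator images, the comparison of methods may be distorted as well. Neither the size nor the net direction of that effect can be determined, so no numerical bias should be claimed. The within-patient comparison remains worth doing. What needs changing is the entry rule, the reporting and the reach of the conclusion.

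**What to change.** 1. Reconcile 6.1, 7.1, 7.2, 7.3 and 9.1 into one entry rule that covers both suspected and known disease, and give 7.3 a category for suspected disease.
2. Use the date of diagnosis and the visit date (12.1.2) to classify each participant by status before the visit: *established diagnosis* or *no diagnosis before the visit*. The second group must include patients imaged for suspicion who prove to have no disease. Defining it by a diagnosis made at the visit would again select on a diagnosis, plausibly one made on that day's conventional images. Healthy volunteers imaged without suspicion also lack a prior diagnosis and should be kept apart, so the reason for imaging should be recorded if the form does not already hold it.
3. Report sensitivity, specificity and the High-Res-OCT versus conventional difference separately for the two groups, with intervals.
4. In 4.1, limit conclusions from established cases and healthy subjects to detection of morphological changes in known disease. Make the diagnostic or replacement statement only as far as the no-prior-diagnosis group supports it.

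The cost is protocol wording, possibly one extra form item and one stratified report, with no additional visit or scan. The downside is that recruitment at follow-up visits may leave the no-prior-diagnosis group small: with 50 diseased patients its sensitivity interval is about ±8.3 points, and the replacement statement may have to be dropped.
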